6.17.2. Psychometric Properties of ASAS-HI

Unless stated otherwise, the analysis population of the psychometric properties of ASAS-HI is ITT Population. The psychometric properties of the ASAS-HI will be evaluated per the following analyses:

- Descriptive statistics for ASAS-HI total score including sample size, mean, median, SD, min, max, % min, % max and % missing, will be provided for the baseline and at Week 16. The number and percentage of ASAS-HI of 0,1,..., and 17 will also be summarized at baseline and at Week 16. Number and percentage of patients with each ASAS-HI item score will also be summarized.
- Item response will be modeled using the Rasch model. The number of parameters in the Rasch model will be selected using likelihood ratio test. Prior to extract item function, model diagnoses, including item fitting and local dependency, will also be conducted. Once a Rasch model is finalized, item function and latent trait will be estimated.
- Differential item functioning (DIF) analyses will be conducted among the demographics groups outlined in Section 6.14.1. Quartiles of latent trait score from the Rasch model will be used to define patients with similar health states.
- Convergent and Discriminant validity will be assessed by Pearson correlation and Spearman rank-based correlation coefficient at baseline and at Week 16 between ASAS-HI total score and other clinical assessments, including BASFI, BASDAI, Spinal Pain, EQ-5D UK Index, SF-36 MCS, SF-36 PCS, Patient Global Assessment. Cohen's conventions (any correlation greater than 0.5 is large, 0.3 to ≤ 0.5 is moderate, 0.1 to < 0.3 is small, and anything smaller than 0.1 is insubstantial) will be used to interpret the results. It is hypothesized there will be small to moderate correlations at baseline and moderate to large correlations at Week 16 between the ASAS-HI and all clinical measures, except for CRP. The correlations between ASAS-HI and CRP at baseline and Week 16 are hypothesized to be small to moderate. Item-level validity will be conducted using biserial correlation and t-test.
- Known Groups validity of ASAS-HI total score will be evaluated using one-way ANOVA with Scheffe's correction for post-hoc pairwise comparison, in distinguishing ASAS-HI scores at baseline between subgroups defined on the basis of ASDAS category: $ASDAS < 2.1$, $2.1 \leq ASDAS \leq 3.5$ and $ASDAS > 3.5$. If the sample size for any ASDAS category is less than 10% of the total sample size, the ASDAS category will be collapsed with lower category.
- Responsiveness will be evaluated by the correlations of ASAS-HI changes from baseline at Week 16 (mBOCF) with changes from baseline in other clinical assessments, including BASFI, BASDAI, ASDAS, and Patient Global Assessment at Week 16 (mBOCF). Moderate to large correlations are hypothesized based on Cohens' conventions. Additionally, responsiveness will be evaluated using one-way ANCOVA comparing mean change in ASAS-HI (mBOCF) between subgroups defined on the basis of (1) ASAS response status at Week 16: not achieving ASAS20; achieving ASAS20 but not ASAS40; and achieving ASAS40, and (2) BASDAI response status at Week 16 (NRI): BASDAI50 nonresponder and BASDAI50 responder, after controlling for baseline

ASAS-HI. Missing ASAS response status will be treated as not achieving ASAS20. It is hypothesized that an overall statistically significant difference will be observed ($p < 0.05$) with at least one statistically significant subgroup comparisons.

- Test-retest reliability will be assessed in stable patients during the interval between screening and baseline assessment (the 2 assessments will be separated by 4 - 42 days). Stable patients will be defined as those with no more than ± 1.5 point difference in BASDAI ratings between screening and baseline. Intraclass correlation coefficients (ICCs) and change scores will be calculated between the initial and retest to evaluate test-retest reliability. An ICC of 0.60 and above is considered acceptable, and an ICC ≥ 0.7 is considered substantial agreement (Nunnally and Bernstein 1994). The analysis population for test-retest reliability will be all patients with both screening and baseline assessments.
- The responder definition of ASAS-HI will be derived using both distribution-based and anchor-based methods. In the distribution-based method, 1.96 and 2.77 times standard error of measurement (SEM) bears statistical significance (Wyrwich 2004) and are considered a threshold for minimal detectable change. The anchor-based method will utilize a logistic model to explore the relationship between ASAS40 response status at Week 16 (NRI) and the change in ASAS-HI from baseline at Week 16 (mBOCF). Model adequacy will be evaluated using Concordance Index. Specificity, sensitivity, Youden index, positive predictive value, negative predictive value, and phi correlation will also be computed at a sequence cut points for change in ASAS-HI. A Receiver Operating Curve (ROC) will be presented to illustrate the trade-off between sensitivity and specificity.
- A cumulative probability plot for change in ASAS-HI from baseline at Week 16 (mBOCF) will be presented by treatment group.

6.17.3. Association between Clinical Outcomes and Health Outcome/Quality-of-Life Measures

The objective of the following analysis is to determine whether greater improvement in clinical outcomes from baseline at Week 16, as assessed by categorized ASAS, BASDAI and ASDAS, is associated with larger improvement from baseline at Week 16 in the following continuous health outcome measurements: ASAS-HI, Fatigue NRS, SF-36 PCS, SF-36 MCS, and WPAI-SpA. Association between clinical outcomes and categorical health outcomes, including SF-36 MCS and SF-36 PCS ≥ 2.5 change from baseline, will also be investigated.

Clinical outcomes will be categorized according to [Table RHBV.6.13](#).

Table RHBV.6.13. Categorization of Clinical Outcomes

Categorization	Clinical Outcomes at Week 16		
	ASAS	BASDAI	ASDAS
(1)	ASAS40 Nonresponder	BASDAI50 Nonresponder	ASDAS at least moderate disease(ASDAS \geq 1.3)
(2)	ASAS40 Responder	BASDAI50 Responder	ASDAS inactive disease (ASDAS <1.3)

Abbreviations: ASAS = Assessment of Spondyloarthritis International Society; BASDAI = Bath Ankylosing Spondylitis Disease Activity Index.

Missing categorical clinical outcomes and continuous health outcomes at Week 16 will be imputed by NRI and mBOCF methodology described in Sections [6.3.1](#) and [6.3.2](#), respectively. Missing categorical health outcomes will also be imputed using NRI method as described in Section [6.3.1](#).

The association analysis will be performed using ITT Population with all treatment groups combined and ITT Population with total ixekizumab groups.

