6.10. Efficacy Analyses

[Table RHBV.6.4](#) includes the description and derivation of the primary and secondary efficacy outcomes.

Sections [6.10.1](#), [6.10.2](#), [6.10.3](#), [6.10.4](#), and [6.10.5](#) summarize the analyses for primary and secondary efficacy measures.

[Table RHBV.6.5](#) provides the detailed analyses including analysis type, method and imputation, population, time point, and treatment group comparisons for primary and secondary efficacy analyses.

Table RHBV.6.4. Description and Derivation of Primary and Secondary Efficacy Outcomes

Measure	Description	Variable	Derivation / Comment	Imputation Approach if with Missing Components
Assessment of Spondyloarthritis International Society 40 (ASAS40), ASAS20, ASAS Partial Remission, ASAS5/6	ASAS40, ASAS20, ASAS Partial Remission and ASAS5/6 are clinical responses derived based on the following ASAS domains (Sieper et al. 2009, ASAS Handbook): 1) Patient Global 2) Spinal Pain 3) Function 4) Inflammation (mean of BASDAI Q5 and Q6) 5) CRP 6) Spinal mobility (lateral spinal flexion)	ASAS40 (Primary Outcome)	The ASAS40 is defined as a $\geq 40\%$ improvement and an absolute improvement from baseline of ≥ 2 units (range 0–10) in ≥ 3 of the following 4 domains (Patient Global, Spinal Pain, Function, and Inflammation) without any worsening in the remaining domain.	See Appendix 3 for derivation of observed response.
		ASAS20 major secondary outcome	An ASAS20 response is defined as a $\geq 20\%$ improvement and an absolute improvement from baseline of ≥ 1 units (range 0–10) in ≥ 3 of the following 4 domains (Patient Global, Spinal Pain, Function, and Inflammation) and no worsening of 20% and ≥ 1 unit (range 0-10) in the remaining domain.	
		ASAS Partial Remission	ASAS partial remission is defined as a value not above 2 units (range 0-10, NRS) in each of the following 4 domains: Patient Global, Spinal Pain, Function, and Inflammation.	
		ASAS5/6	ASAS5/6 includes assessment of all 6 individual ASAS domains (Patient Global, Spinal Pain, Function, Inflammation, CRP, Spinal mobility) and represents improvement of $\geq 20\%$ in at least 5 domains.	
Patient Global (Assessment of Disease Activity)	From the ASAS handbook (Sieper et al. 2009), the patient is asked to respond to the following question: “How active was your spondylitis on average during the last week?”	Patient Global, NRS	Range: 0 to 10 “0” (not active) and “10” (very active).	Single item, missing if missing

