		BASDAI score	BASDAI = (Q1+Q2+Q3+Q4+inflammation)/5 Range: 0 to 10 “0” (none) and “10” (very severe).	If only Q6 is missing, BASDAI is average of the other 5 questions; missing BASDAI if more missing than just Q6.
		BASDAI and inflammation change from baseline and % improvement from baseline	Change from baseline calculated as: observed score – baseline score % improvement from baseline calculated as: $100 \times \frac{\text{Baseline} - \text{Observed score}}{\text{Baseline}}$	Missing if baseline or observed value is missing
		BASDAI50 – major secondary outcome	BASDAI50 represents an improvement of ≥50% of the BASDAI score from baseline, ie, if the value of % improvement from baseline is ≥50, BASDAI50	Missing if observed value is missing (note: baseline BASDAI is part of inclusion

Measure	Description	Variable	Derivation / Comment	Imputation Approach if with Missing Components
			is met.	criteria therefore should not be missing)
Bath Ankylosing Spondylitis Functional Index (BASFI)	The BASFI establishes a patient’s functional baseline and subsequent response to treatment (Calin et al. 1995). To complete the BASFI, a patient will be asked to rate the difficulty associated with 10 individual basic functional activities. Patients respond to each question using a NRS (range 0 to 10), with a higher score indicating worse functioning.	BASFI score	BASFI score is the mean of the 10 item scores completed on a NRS Range: 0 to 10 “0” (easy) and “10” (impossible).	Missing if >20% scores (ie, >2 of the 10 item scores) are missing
		BASFI change from baseline – major secondary outcome % improvement from baseline	Change from baseline calculated as: observed BASFI – baseline BASFI % improvement from baseline calculated as: $100 \times \frac{Baseline - Observed\ score}{Baseline}$	Missing if baseline or observed value is missing.
High Sensitivity C-Reactive Protein (CRP)	High sensitivity CRP will be the measure of acute phase reactant. It will be measured with a high sensitivity assay at the central laboratory to help assess the effect of ixekizumab on disease activity.	CRP value	Lab values obtained from central lab	Missing if missing
		CRP change from baseline	Change from baseline calculated as: observed CRP – baseline CRP	Missing if observed value is missing (note: if V2 CRP is missing, V1 CRP will be used as baseline).
		CRP ratio of postbaseline to baseline	Calculated as: observed CRP / baseline CRP	

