Ankylosing Spondylitis Disease Activity Score (ASDAS)	The ASDAS is a composite index to assess disease activity in AS (Machado et al. 2011a, 2011b; Zochling 2011). The parameters used for the ASDAS (with CRP as acute phase reactant): 1) Total back pain (BASDAI Q2) 2) Patient global 3) Peripheral pain/swelling	ASDAS _{crp}	ASDAS _{crp} (Sieper et al. 2009): $0.121 \times \text{total back pain} + 0.110 \times \text{patient global} + 0.073 \times \text{peripheral pain/swelling} + 0.058 \times \text{duration of morning stiffness} + 0.579 \times \text{Ln}(\text{CRP}+1)$ (Machado et al. 2015). C-reactive protein is in mg/liter, the range of other variables is from 0 to 10; Ln represents the natural logarithm.	Missing if any of the components is missing. If CRP <2 mg/L or below the limit of detection, then use 2 mg/L in the calculation (Machado et al. 2015).
		ASDAS _{crp} change from baseline - major secondary	Calculated as: observed ASDAS – baseline ASDAS	Missing if baseline or observed value is missing

Measure	Description	Variable	Derivation / Comment	Imputation Approach if with Missing Components
	(BASDAI Q3) 4) Duration of morning stiffness (BASDAI Q6) 5) CRP in mg/L	outcome		
		ASDAS Disease Activity States	Four (4) disease activity states have been defined by ASAS consensus (Machado et al. 2011c, Machado 2018): 
 • ASDAS <1.3 defines inactive disease • $1.3 \leq \text{ASDAS} < 2.1$ defines low disease activity • $2.1 \leq \text{ASDAS} \leq 3.5$ defines high disease activity • ASDAS >3.5 defines very high disease activity. 	Set the disease activity state to worst state (ie, very high) if observed ASDAS score is missing
		ASDAS<2.1	Defined as ASDAS <2.1 (low or inactive disease activity)	
		Clinical important improvement	Defined as at least 1.1 unit change in ASDAS from baseline	Missing if baseline or observed ASDAS score is missing
		Major improvement	Defined as at least 2.0 unit change in ASDAS from baseline or reached the minimum of ASDAS score (0.6361) at postbaseline visit	

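### SAP 6.17.3 asks about ASDAS improvement, but Table RHBV.6.13 groups ASDAS by attained Week 16 state, so large improvers with a high baseline can fall in the lower category

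*SAP*

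**What the plan says.** Section 6.17.3 of the SAP (association between clinical outcomes and health outcome/quality-of-life measures) states its aim as finding out "whether greater improvement in clinical outcomes from baseline at Week 16, as assessed by categorized ASAS, BASDAI and ASDAS", is associated with larger Week 16 improvement in ASAS-HI, Fatigue NRS, SF-36 PCS, SF-36 MCS and WPAI-SpA. It is run in all arms combined and in the total ixekizumab group.

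Table RHBV.6.13 then defines two categories for each clinical outcome:

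- **ASAS:** ASAS40 nonresponder or responder. Table RHBV.6.4 builds ASAS40 on a 40% "improvement and an absolute improvement from baseline of" at least 2 units, so it measures change.
- **BASDAI:** BASDAI50 nonresponder or responder. In Table RHBV.6.4, "BASDAI50 represents an improvement of ≥50% of the BASDAI score from baseline", so this also measures change.
- **ASDAS:** the lower category is "ASDAS at least moderate disease" (1.3 or above) and the upper is "ASDAS inactive disease (ASDAS <1.3"). Neither refers to baseline.

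Table RHBV.6.4 already holds change-based ASDAS variables. Clinically important improvement is "Defined as at least 1.1 unit change in ASDAS from baseline". Major improvement is "Defined as at least 2.0 unit change in ASDAS from baseline or reached the minimum of ASDAS score (0.6361) at postbaseline visit". Table RHBV.6.13 uses neither.

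**The concern.** The aim names improvement from baseline for all three clinical outcomes, and one of the three grouping variables does not measure it. Whether a patient ends below 1.3 depends on how far the score fell and also on where it began. A large fall from a high baseline can miss the cut, and a modest fall from a low baseline can make it.

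At stake is how an exploratory result would be read. A report could present the ASDAS contrast as evidence about improvement when it partly reflects baseline disease activity. Grouping large improvers with non-improvers would also tend to shrink the apparent association.

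**Working it through.** **1. The plan's own figure.** The stated ASDAS minimum is 0.6361. With all four items at 0 and CRP set to the 2 mg/L floor ("If CRP <2 mg/L or below the limit of detection, then use 2 mg/L in the calculation"), the SAP formula gives 0.579 × ln(2 + 1) = 0.6361. It reproduces.

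**2. What the thresholds imply.** To reach the upper category the fall must exceed (baseline − 1.3).

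| Baseline ASDAS | Fall needed to be below 1.3 |
|---|---|
| 2.5 | more than 1.2 |
| 3.0 | more than 1.7 |
| 3.3 | more than 2.0 |
| 3.5 | more than 2.2 |
| 4.0 | more than 2.7 |
| 4.5 | more than 3.2 |

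Since 3.3 − 2.0 = 1.3, a patient starting at 3.3 or above can fall by exactly 2.0 and stay in the lower category. Going from 4.0 to 1.9 is a fall of 2.1, which is major improvement, but it is placed in category (1). Going from 2.5 to 1.2 is a fall of only 1.3, but it is placed in category (2).

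**3. Are such baselines possible for eligible patients?** The four item weights sum to 0.121 + 0.110 + 0.073 + 0.058 = 0.362.

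- All items at 4, CRP at the floor: 4 × 0.362 + 0.636 = 2.08.
- All items at 6.3, CRP 5 mg/L: 6.3 × 0.362 + 0.579 × ln(6) = 2.281 + 1.037 = 3.32.

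The first profile sits at the BASDAI and back-pain entry thresholds of 4. Both are illustrations, not expected values.

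**4. How many patients?** Neither document gives a baseline ASDAS distribution, an expected change or an expected inactive-disease rate, so every figure in this step rests on assumptions.

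*Single-group grid.* Baseline SD 0.7–0.9, change SD 0.8–1.0, baseline–change correlation −0.4, mean change −0.5 to −2.0, major improvement as in Table RHBV.6.4. Share of major improvers placed in category (1):

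| Baseline mean | Share in category (1) |
|---|---|
| 3.0 | 18–41% (11–19% if mean change is −2.0) |
| 3.3 | 22–64% |
| 3.6 | 36–82% |
| 3.8 | 47–89% |
| 4.0 | 57–94% |

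*Mixture of placebo and active arms.* Mean change −0.4 or −0.5 on placebo and −1.3 or −1.5 on active, change SD 1.0, baseline SD 0.7–0.8, baseline–change correlation 0 or −0.4. Among patients with a fall of 2.0 or more, 24–34% are in category (1) at a baseline mean of 3.0 and about 40–68% at 3.6–3.8. A rerun with SD 0.7 and zero correlation takes the lower end at 3.0 to about 20%.

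The mixture figures count falls of 2.0 or more. Adding patients who qualify only by reaching the minimum score lowers the share, because they are always below 1.3. In the grid with baseline SD 0.7, mean change −1.0 and change SD 1.0, it goes from 33% to 25% at a baseline mean of 3.0, and from 63% to 61% at 3.6.

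**5. Effect on the association.** Take the mixture at 3.6–3.8 and assume a correlation of 0.6 between ASDAS change and health-outcome change. The difference in health-outcome change between the two categories is 0.71–0.88 SD with the below-1.3 split, against 0.96–0.98 SD with a split at a 1.1-unit fall. The attenuation runs from 1 − 0.88/0.96 = 8% to 1 − 0.71/0.97 = 27%.

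**6. Cover elsewhere.** The responsiveness analyses in SAP 6.17.1 and 6.17.2 correlate change in Fatigue NRS and in ASAS-HI with change in ASDAS. No such analysis is planned for SF-36 PCS, SF-36 MCS or WPAI-SpA.

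**The case against.** The other side has several good points.

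- **The cut is open and prespecified.** ASDAS inactive disease is a major secondary endpoint. The table states the threshold and labels the lower row as a disease state, not as non-improvement. A careful reader can see what is compared. This stands, but it does not make a state into a change.
- **Nearly everyone in the upper category has improved.** At assumed baseline means of 3.6–3.8, 93–98% of the inactive group had a fall of at least 1.1. Being inactive with a smaller fall needs a baseline below 1.3 + 1.1 = 2.4, which is near the bottom of the eligible range. Misplacement is therefore mostly one-sided. This stands.
- **The association would still be seen.** In those scenarios the difference is about 4.5–6.3 standard errors from zero at n = 320. The ixekizumab-only analysis has about half the patients.
- **Two of the five health outcomes are already served** by correlations with continuous ASDAS change, which avoid dichotomising. This stands and narrows the gap to three.
- **Rewording the aim would also remove the mismatch.** True, but SF-36 and WPAI-SpA would still have no analysis against ASDAS improvement.

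A reader might go further and infer that most large improvers are grouped with non-improvers. The documents do not support that. They contain no ASDAS distribution, and the share moves from a minority at a baseline mean of 3.0 to a majority at 4.0. A reader might also infer that the ASDAS question goes unanswered. That is too strong as well: under the assumptions above the association is weakened, not lost.

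**Conclusion.** The mismatch is real and can be read directly from the SAP: the aim concerns improvement, and the ASDAS grouping uses only the attained state. It follows from the SAP's own thresholds, with no distributional assumption, that patients starting at 3.3 or above can meet the 2.0-unit criterion and remain in the lower category. The contrast therefore mixes improvement with baseline level.

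The size is uncertain. The misplaced share and the 8–27% attenuation at baseline means of 3.6–3.8 depend on assumed baseline, change and correlation values. The direction, towards a weaker association, is likely but not certain.

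Severity is minor. Section 6.17 is exploratory, and the primary and major secondary tests are untouched.

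**What to change.** In Table RHBV.6.13:

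- add ASDAS clinically important improvement (fall of at least 1.1), no/yes;
- add ASDAS major improvement as defined in Table RHBV.6.4, no/yes;
- keep the prespecified inactive-disease split as its own row, labelled attained disease state, rather than replacing it.

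The SAP revision history says that Version 3 was approved after unblinding, so the added rows should be recorded as introduced after unblinding.

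The cost is one table edit and a few extra exploratory outputs. Both variables are already derived, and no new data are needed.

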6.17.4. Planned Exploratory Health Outcome/Quality-of-Life Analyses

[Table RHBV.6.14](#) includes the description and derivation of the exploratory health outcomes and QOL measures.

[Table RHBV.6.15](#) provides the detailed analyses including analysis type, method and imputation, population, time point, and treatment group comparisons for the exploratory health outcomes and QOL analyses.

Table RHBV.6.14. Description and Derivation of Exploratory Health Outcomes and Quality-of-Life Measures

Measure	Description	Variable	Derivation / Comment	Missing Items
European Quality of Life – 5 Dimensions 5 Level	
EQ-5D-5L: is a standardized measure of health status used to provide a simple, generic measure of health for clinical and economic appraisal. The EQ-5D-5L consists of 2 components: a descriptive system of the respondent’s health and a rating of his/her current health state using a 0- to 100-mm VAS. The descriptive system comprises the following 5 dimensions:
 
 item 1: mobility item 2: self-care item 3: usual activities item 4: pain/discomfort item 5: anxiety/depression 
The respondent is asked to indicate his/her health state by ticking (or placing a cross) in the box associated with the most appropriate statement in each of the 5 dimensions.
	
EQ-5D mobility, EQ-5D self-care, EQ-5D usual activities, EQ-5D pain/ discomfort, EQ-5D anxiety/ depression
	
Five health profile dimensions, each dimension has 5 levels: 1 = no problems 2 = slight problems 3 = moderate problems 4 = severe problems 5 = extreme problems
 
It should be noted that the numerals 1 to 5 have no arithmetic properties and should not be used as a primary score.
	
Each dimension is a single item, missing if missing.

		
EQ-5D-5L UK Population-based index score
	
Uses the concatenation of the value of each EQ-5D-5L dimension score in the order: item1; item2; item3; item4; item5. Derive EQ-5D-5L UK Population-based index score according to the link by using the UK algorithm (Szende et al. 2007) to produce a patient-level index score between -0.59 and 1.0 (continuous variable): http://www.euroqol.org/fileadmin/user_upload/Documenten/Excel/Crosswalk_5L/EQ-5D-5L_Crosswalk_Value_Sets.xls
	
If any of the items is missing, the index score is missing

	
The VAS records the respondent’s self-rated health on a vertical VAS where the endpoints are labeled 100 = “best imaginable health state” and 0 = “worst imaginable health state”.
	
EQ-5D VAS
	
Range from 0 = “worst imaginable health state” to 100 = “best imaginable health state”. Note: higher value indicates better health state.
	
Single item, missing if missing

Healthcare Resource Utilization	
Healthcare resource utilization data regarding the number of visits to medical care providers, such as general
	
Visits to medical care providers (except hospitals)
	
Derivation will be performed within each treatment period
	
NA

		
Days in hospital
		

Measure	Description	Variable	Derivation / Comment	Missing Items
	practitioners, specialists, physical, or occupational therapists, and other nonphysical care providers for services outside of the clinical trial; emergency room admissions; hospital admissions; and concomitant medications will be recorded by the investigator in the study's CRF.	Number of hospital admissions (Medical ICU, surgical ICU, coronary ICU, general ward, trauma unit, unknown or other)		
		Healthcare providers (type of specialist for healthcare practitioner)		

Abbreviations: EQ-5D-5L = European Quality of Life – 5 Dimensions 5 Level; ICU = intensive care unit; UK = United Kingdom; VAS = visual analog scale.

Table RHBV.6.15. Description of Exploratory Health Outcomes and Quality-of-Life Analyses

Measure	Variable	Analysis Method (Sections 6.1 and 6.3)	Population (Section 6.1.5)	Comparison / Time Point
EQ-5D-5L	EQ-5D mobility, EQ-5D self-care, EQ-5D usual activities, EQ-5D pain/discomfort, EQ-5D anxiety/depression	For each EQ-5D dimension, the proportion of patients with “no problems” will be analyzed by: Logistic regression analysis with NRI; Fisher’s exact test with NRI	ITT Population	IXE80Q2W & IXE80Q4W vs. placebo at Week 16
		Descriptive statistics of each category and proportion of patients with “no problems”	Extended Treatment Period Population	IXE80Q2W & IXE80Q4W during Period 3
	Change from baseline in: EQ-5D-5L UK Population-based index score, EQ-5D VAS	ANCOVA with mBOCF	ITT Population	IXE80Q2W & IXE80Q4W vs. placebo at Week 16
		Descriptive statistics of change from baseline	Extended Treatment Period Population	IXE80Q2W & IXE80Q4W during Period 3
Healthcare Resource Utilization	Visits to medical care provider; Days in Hospital; Number of hospital admissions; Healthcare provider	Descriptive statistics	ITT Population	overall comparison in Period 2 by Kruskal Wallis test
		Descriptive statistics	Extended Treatment Period Population	IXE80Q2W & IXE80Q4W during Period 3

Abbreviations: ANCOVA = analysis of covariance; EQ-5D-5L = European Quality of Life – 5 Dimensions 5 Level; ITT = intent-to-treat; IXE80Q2W = ixekizumab 80 mg every 2 weeks; IXE80Q4W = ixekizumab 80 mg every 4 weeks; mBOCF = modified baseline observation carried forward; NRI = nonresponder imputation; UK = United Kingdom; VAS = visual analog scale.

